1. BACKGROUND AND SIGNIFICANCE

As concerns regarding the effects of agriculture on human and environmental health mount^{1,2}, a growing number of farmers are seeking ways to improve health from the ground up. A promising way by which a growing number farmers are seeking to improve environmental health is by using agro-ecological practices (i.e., farming more closely in harmony with natural systems), which include practices such as multi-cropping, ley rotations, and/or integrated crop-livestock systems³. When properly implemented, agro-ecological practices can improve soil health, nutrient cycling, and biodiversity above and below ground³⁻⁵. Despite potential major ecological benefits, we lack critical knowledge if consuming foods from agro-ecological systems also benefits human health. The purpose of this project is to test the hypothesis that consuming foods produced using agro-ecological practices improves consumer health compared to consuming similar foods from conventional (monoculture) farming systems.

This work will utilize a randomized cross-over design to compare an agroecological vs conventional sourced diet, and determine their effects on inflammation and cardio metabolic health signatures in middle-aged adults (35-60 y old). Diets will be isocaloric and matched for macronutrient content, and consumed for 44 days each with a 14-day washout (habitual diet) period in between. Blood, urine, and stool samples will be obtained before and after the dietary interventions, in addition to data about physical activity and questionnaires regarding quality of life.

2. STUDY OBJECTIVES

1. To determine the effects on **plasma inflammatory markers (IL-6, TNF- α , C-reactive protein, and VCAM-1)** before and after each dietary intervention.
2. To determine effects on **urinary and plasma metabolites (vitamin and mineral derivatives, polyphenols, amino acids, glucose metabolites etc.)** to provide insight into metabolic health pathways before and after each dietary intervention.
3. To determine effects on **gut microbiota communities** (alpha and beta diversity, and short-chain fatty acid producing bacteria) before and after each dietary intervention.

3. DESIGN AND PROCEDURES

3.1 Study duration

Total involvement for each participant will be 16 weeks. Each diet will be followed for 44 days (4 day rotating menus x 11 periods) with a 14-day washout period in between.

3.2 Participants

We will include a total of 40 middle aged adults (35-60 years) of all races and ethnicities in this study. Inclusion/exclusion criteria are listed below.

Inclusion criteria:

- Age ≥ 35 and ≤ 60 years;
- BMI ≥ 25 and ≤ 35 kg/m²;
- Weight stable in last 3 months (loss or gain $<4\%$);
- Hemoglobin A1C (HbA1C $\leq 6.4\%$);
- Fasting plasma glucose concentration <126 mg/dl;
- For the safety of the participant and proper consent of the procedures, subjects must be able to speak and understand English to participate in this study;
- Stable medication/supplement use for 3 months prior to study;

Exclusion criteria:

- Use of medications that are known to affect the study outcome measures (e.g., NSAIDs, corticosteroids) or increase the risk of study procedures (e.g., anticoagulants) that cannot be temporarily discontinued for this study;
- Strict dietary patterns (e.g., vegan, keto);
- Consuming >14 alcoholic drinks per week;
- Use of cigarettes (or other tobacco products) in last 3 months;
- Engaged in high level of competitive exercise (e.g., iron man, marathons, powerlifting);
- Diagnoses of active malignancy, congestive heart failure, diabetes mellitus or chronic obstructive pulmonary disease;
- Any inflammatory diseases (e.g., autoimmune diseases, coeliac disease, glomerulonephritis, hepatitis, inflammatory bowel disease, arthritis);
- Use of antibiotics in last 60 days;
- Pregnant or planning to become pregnant in the next 5 months;
- Lactating women;
- Persons who are unable or unwilling to follow the study protocol or who, for any reason, the research team considers not an appropriate candidate for this study, including non-compliance with screening appointments or study visits.

* Participants that are pregnant or planning on becoming pregnant in the next 5 months are excluded. The justification is the documented alterations in metabolism that occur during pregnancy ⁶, which would impact our metabolomics analysis in this study.

Exclusion criteria will primarily be identified by way of a phone/email screen and routine bloodwork (when determined eligible based on the phone-screen and/or email-screen and after being consented).

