Consent Visit (Week 1. Duration: 1 hour): This visit can be done virtually through Zoom or occur in person in the Center for Human Nutrition Studies (CHNS) at Utah State University. Potential subjects will attend a consent session conducted by a trained member of the research staff to present the details of the study. Interested participants will complete the informed consent process privately with study staff. We will allow up to 60 minutes for the subjects to read the consent and ask questions. If a subject wants additional time to think about the study, this will be allowed. The study team will contact the subject three days after the initial consent visit ask if he or she has come to a decision. No study procedures will take place before written consent is obtained. To minimize subject burden, participants will be instructed during the phone screen that they have the opportunity to combine the consent visit with their screening visit (see below). If participants wish to combine visits, they are instructed that they will have to perform this visit in the morning after an overnight, 12-hour fast.

Screening Visit (Week 1. Duration: 2 hours): Study participants will be asked to come in during the morning after an overnight, 12-hour fast. During this visit the following will take place:

- **Blood Draw:** A trained phlebotomist (the PI) will draw a fasted blood sample for routine blood work to ensure the participant qualifies for the study. Using a small needle, 15 ml blood will be collected from a vein in the participant's forearm or hand. Blood samples will be sent to LabCorp to be analyzed for HbA1C, Glucose, Basic Metabolic Panel (BMP), and Lipid panel. The blood of women of childbearing potential will be subject to a pregnancy test (hCG) as part of this screening blood draw. This will also occur through LabCorp.
- **Body mass and height.** Height (cm) will be measured without shoes. Body mass (kg) will be measured without shoes, coats, or sweaters. BMI will be calculated as body mass (kg) / height (m)².
- **Blood pressure:** A blood pressure measurement will be taken using an automated upper arm blood pressure monitor (Omron BP5250). A total of three measurements will be taken and the average value of those will be collected for participant characterization.
- **Questionnaires:** Participants will be asked to complete the following questionnaires:

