- **Blood Draw**: A trained phlebotomist (the PI) will draw a fasted blood sample for metabolomics and inflammatory biomarker assays. A total of 15 mL of blood (1 TBPS) will be drawn. Our plans for measuring cytokines and metabolites are discussed in the *Analytical Procedures and Statistical Considerations subsection* (see below).

Intervention (44 days x 2 diets; 1 hour per week): After completing all baseline testing, participants will be randomized to one of the two starting diets (agroecological or conventional, for 44 days with a 14 day washout period until they start their second diet (agroecological or conventional depending on the starting diet). In accordance with established protocols, a research dietitian will provide weight-maintenance diets with a macronutrient distribution of 20% protein, 30% fat, and 50% carbohydrate based on each individual's daily energy requirement (Harris-Benedict equation). All foods that participants consume during those 4-weeks will be provided by the Metabolic Kitchen at NDFS, and dietitian-led group classes and handouts with food preparation instructions will be provided to the participants to ensure compliance. The diets will be provided as 4-day rotating menus and participants will be asked to pick-up food twice weekly at the NDFS building. This will allow the research time to interact face-to-face with the participant, address any issues, and further ensure compliance. All subjects assigned to the same diet will receive identical meals and snacks, but portion sizes will be determined based on the previously mentioned daily energy requirement. Food for the agroecological diet will be sourced predominantly from the Greenacres farm (Cincinnati, OH) and food for the conventional diet

will be sourced from local grocery stores (non-organic produce). All foods will be stored in food-grade fridges and freezers in the CHNS Metabolic Kitchen and food boxes will be prepared weekly by staff. Examples of the diets are presented in **Table 2**.

Table 2: Examples of Meals

Breakfast	Whole milk, eggs, oatmeal, and blueberries
Snack	Rice cakes
Lunch	Ground beef, tomato salad and cherries
Snack	Apple with nut butter
Dinner	Grilled chicken with rice and steamed broccoli

Additionally, subjects will complete the following study procedures during each intervention period:

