- **Sleep, diet, and activity logs:** We will ask participants to maintain their habitual sleep levels. Participants will be asked to log their wake-up and sleep time as well as the time they spend doing physical activity in RedCap. Participants will be provided a daily link and/or reminded by phone (only if they forgot to fill these out).
- **Stool and urine samples:** Additional stool and urine samples will be collected at the end and beginning of each dietary period, using a similar approach as described in the *baseline visit 1* subsection,
- **Activity:** We will ask participants to maintain their habitual physical activity levels. A commercial Garmin activity monitor will be worn 24 hr/d to record total daily steps as a measure of physical activity. The activity monitor will connect via Bluetooth to the participant's personal smartphone or other internet-connected device loaded with the Garmin Connect app. Data will be stored in individual study accounts on the Garmin website where the study team will be able to access and review activity and monitor device function and provide feedback and encouragement to participants.

Post Diet Visits 1-2 (Weeks 8 & 16; 1 hour): On the last day of each nutrition intervention/diet phase, participants will be asked to come to the CHNS building at Utah State University to undergo a fasted blood draw (30 mL), and to complete questionnaires to determine intervention effects. The blood will be used for cytokines and metabolites and for routine blood samples analysis by LabCorp as described in the *screening visit subsection*. The questionnaires involved include the Perceived Stress Scale (PSS), Short Form Healthy Survey (SF-36), Profile of Mood States (POMS), and the Pittsburgh Sleep Quality Index (PSQI).

Baseline Visit 2 (weeks 8; 1 hour): At the beginning of the second 44-day dietary intervention period, participants will report to the lab facilities within the Center for Human Nutrition at Utah State University after an overnight fast (no eating or drinking except water for 12 h). Participants will be asked to collect fasting urine and first-of-the-day stool samples the morning before coming in, and will undergo a fasted blood draw (30 mL) while in the lab. The blood will be

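### Section 3.2 lets anticoagulant users join by pausing the drug to make five ordinary vein draws safer; current users should be excluded outright instead

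*Combined protocol and SAP*

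**What the plan says.** The relevant exclusion criterion in Section 3.2 covers two kinds of drug. The first may affect the outcome measures, with NSAIDs and corticosteroids as examples. The second may "increase the risk of study procedures (e.g., anticoagulants) that cannot be temporarily discontinued for this study". Both share the closing condition, so a user of either kind is excluded only if the drug cannot be paused. The criterion does not say how long a pause lasts, who decides that it is acceptable, or when the drug is restarted. Section 3.2 also has an inclusion rule: "Stable medication/supplement use for 3 months prior to study".

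The timetable is in Section 3.1: "Each diet will be followed for 44 days (4 day rotating menus x 11 periods) with a 14-day washout period in between".

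Section 3.4 describes the blood draws:
- Screening: "Using a small needle, 15 ml blood will be collected from a vein".
- Baseline Visit 1: "A total of 15 mL of blood (1 TBPS) will be drawn".
- Each of the two post-diet visits: participants "undergo a fasted blood draw (30 mL), and to complete questionnaires to determine intervention effects".
- Baseline Visit 2: a further 30 mL.

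Section 5 lists the hazards of the draws as bruising, some discomfort, infection on rare occasions, and light-headedness or fainting. It does not discuss stopping a drug. It also says that participants gain nothing beyond the satisfaction of contributing, although they do receive their laboratory results. Section 6 offers immediate care after a study injury, but no free treatment or payment for it.

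**The concern.** An anticoagulant is taken to prevent clots, and a clot is far more serious than bleeding at a needle site. The criterion accepts the larger hazard to reduce the smaller one. By the plan's own wording anticoagulants are listed for procedure risk and not for an effect on the outcomes, and none of the three objectives in Section 2 needs anyone to be off the drug. At stake is the safety of any individual who enrols this way, in a study that offers no direct benefit. The diet comparison itself is not at stake.

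**Working it through.** **1. Diet length.** The plan's own figure reproduces: a 4-day menu × 11 periods = 44 days.

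**2. What the pause protects against.** Draws from Section 3.4:

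| Visit | Volume (mL) |
|---|---|
| Screening | 15 |
| Baseline 1 | 15 |
| Post diet 1 | 30 |
| Baseline 2 | 30 |
| Post diet 2 | 30 |
| **Total, 5 draws** | **120** |

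No other procedure in the documents breaks the skin. Stool and urine are collected at home; the remainder are questionnaires, logs, weight, height, blood pressure and an activity monitor. Of the hazards in Section 5, bruising is the one that coming off an anticoagulant could plausibly lessen.

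**3. How long the pause might be.** The documents give no figure, so there are two readings.
- Held through both diets, from Baseline 1 to Post diet 2: 44 + 14 + 44 = 102 days. Four of the five draws fall in this span; the screening draw comes before it.
- Held only around each draw: at an assumed 2 to 5 days per draw, 5 × 2 = 10 to 5 × 5 = 25 days.

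**4. Illustrative clot risk.** The documents give no rate. Take an assumed excess risk off the drug of r per year, constant over time. The risk per person is 1 − exp(−r × days/365).

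| Assumed r | 10 days | 25 days | 102 days |
|---|---|---|---|
| 1% a year | 0.03% | 0.07% | 0.28% |
| 5% a year | 0.14% | 0.34% | 1.4% |
| 10% a year | 0.27% | 0.68% | 2.8% |

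For example, 1 − exp(−0.05 × 102/365) = 0.0139. These figures show only how the risk scales with the length of the pause; they do not estimate this trial's risk. The higher rates apply to the people least likely to be judged able to stop.

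**5. Cost of exclusion.** The number of users is not given. If one or two of the 40 planned participants were users, excluding them would remove 1/40 = 2.5% to 2/40 = 5% of enrolment.

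**The case against.** The strongest reply is that this is an exclusion criterion and not an instruction. Nothing in the documents tells anyone to stop a drug. For an anticoagulant, being unable to stop plausibly includes being unable to stop safely, so the clause may already remove most people at real risk. Section 3.2 also lets the team refuse any candidate it considers unsuitable. This has force, and it is why the number affected may be zero. It does not supply a reason for the remaining users to stop: they would still give up protection for a small gain at five vein draws.

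Four stronger readings are tempting but are not supported.

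- *That the plan calls for 102 days off the drug.* The text calls the pause temporary and sets no length. Because the stated reason is procedure risk, a short hold around each draw fits at least as well.
- *That the pause must start before consent, or three months before the study.* Section 3.4 says that "No study procedures will take place before written consent is obtained" and tells candidates that "they have the opportunity to combine the consent visit with their screening visit". Combining the visits is optional, and a single 15 mL draw on the drug is a small matter. Nothing asks anyone to stop early to meet the stable-medication rule; someone who stops at entry may simply fail that rule.
- *That the draws carry no more than a bruising risk for these people.* Section 5 describes participants in general and does not address anticoagulant users, whose bleeding risk may be higher. The judgement that the gain is small rests on the nature of the procedure, not on a figure in the plan.
- *That no clinician oversight exists.* The supplied text requires no prescriber approval, but the phone script is not supplied and consent pages were removed. They may contain a safeguard. Even with one, the criterion would still offer the pause as a route into the study.

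**Conclusion.** The point holds as a minor to moderate participant-safety improvement. As written, Section 3.2 allows an anticoagulant user to enrol by pausing the drug, and the only benefit is less bleeding at five draws totalling 120 mL. The pause could run from a few days per draw to 102 days, and some clot risk is taken on at either end of that range. The conclusion does not depend on the assumed rates or on the 102-day reading. It needs only that a clot is worse than needle-site bleeding and that the study's purposes do not require the pause. The number affected is unknown and may be none.

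A reader might go on to infer that the trial's results or power are affected. The documents give no basis for that. The NSAID and corticosteroid part of the clause is outside this point, because the plan's reason there is the outcome measures.

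**What to change.** In Section 3.2, remove anticoagulants from the clause that allows a temporary pause and add current anticoagulant use as an exclusion in its own right. Leave the clause unchanged for NSAIDs and corticosteroids. Study-caused time off an anticoagulant then falls to zero on either reading.

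The cost is one clause and possibly a volunteer or two. Section 4.1 expects only about 30 people to be consented, so each one counts a little.

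A second option is to let users stay on a dose that meets the stable-medication rule, with longer pressure on the draw site. It is less simple: it needs a clinician to agree that the drug is compatible with a fully provided diet, and it assumes that drug and diet do not interact on the outcomes. Outright exclusion avoids both issues and is preferred.

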3.3 Study Schedule

ACTIVITY/VISIT	WEEK	DURATION
PHONE SCREEN A scripted phone screen will be performed to determine pre-eligibility prior to consent.	1	15 min
CONSENT A one-on-one consent visit will be conducted privately with staff either in-person or via Zoom.	1	1 h
SCREENING This visit will take place in the morning after an overnight fast and will have the following procedures: informed consent, screening blood draw (including serum pregnancy test for women of child-bearing potential), health history, height and weight, and screening questionnaires regarding food intake, health, and sleep.	1	2 h
BASELINE VISIT DIET 1 This visit will take place in the morning after an overnight fast. Participants will be asked to complete a fasted blood draw and questionnaires, and bring in urine and stool samples that were collected using at-home collection kits.	2	1 h
INTERVENTION DIET 1 Participants will be randomized to consume one of the following sourced diets: agroecological or conventional. They will follow this nutrition pattern for 44 days. During this time, participants will come to the NDFS building twice a week to pick up food.	2-8	1 h per week
POST VISIT DIET 1 On the last day of diet 1, participants will be asked to complete a fasted blood draw and questionnaires, and bring in urine and stool samples that were collected using at-home collection kits.	8	1 h
WASHOUT PERIOD Participants will consume self-selected (habitual) diets for 14 days. No involvement from research team.	9-10	none
BASELINE VISIT DIET 2 This visit will take place in the morning and will have a fasted blood draw. Participants are also asked to bring in stool and urine samples that were collected using at-home collection kits.	10	1 h
INTERVENTION DIET 2 Participants will now start their second nutritional intervention (agroecological or conventional sourced diet depending on the diet consumed during the first intervention). During this time, participants will come to the NDFS building twice a week to pick up food.	10-16	1 h per week

POST VISIT DIET 2 On the last day of diet 2, participants will be asked to complete a fasted blood draw and questionnaires, and bring in urine and stool samples that were collected using at-home collection kits.	16	1 h
---	----	-----

3.4 Description of study visits

Participants will be asked to complete four testing visits throughout their participation in the study (pre and post visits for each of the diets) as well as complete two on-site visits per week during each of the 44-day dietary intervention periods to consume a meal and obtain a current body weight measurement. All visits will take place in clinical research space located at the Center for Human Nutrition Studies (CHNS), except for food pickup, which will take place at the NDFS building.

Phone Screen (Week 1. Duration: 15 min): Interested participants will be pre-screened by telephone, using a scripted list of questions (attached) to identify individuals that may be eligible for study entry. Suitable candidates will then be provided a REDCap survey link to complete additional screening questions that asks them further details about their health, dietary habits, and sleep habits (see inclusion/exclusion criteria). Only the minimum PHI will be collected to determine eligibility. Responses will be reviewed by a study team member (all study team members will have completed the necessary CITI training) and potentially eligible candidates will be contacted to schedule a consent/screening visit. The pre-screen is put in place to confirm that the participant meets most of the inclusion/exclusion criteria before the subject is scheduled for a consent meeting. The phone screen is thus performed to limit the amount of ineligible research participants that are consented/screened that could easily be excluded by means of a phone screening. This would also provide interested participants with the opportunity to ask additional questions about the study and to determine if they are interested in moving forward with a consent/screening visit. This will limit both subject and research staff time burden.

Consent Visit (Week 1. Duration: 1 hour): This visit can be done virtually through Zoom or occur in person in the Center for Human Nutrition Studies (CHNS) at Utah State University. Potential subjects will attend a consent session conducted by a trained member of the research staff to present the details of the study. Interested participants will complete the informed consent process privately with study staff. We will allow up to 60 minutes for the subjects to read the consent and ask questions. If a subject wants additional time to think about the study, this will be allowed. The study team will contact the subject three days after the initial consent visit ask if he or she has come to a decision. No study procedures will take place before written consent is obtained. To minimize subject burden, participants will be instructed during the phone screen that they have the opportunity to combine the consent visit with their screening visit (see below). If participants wish to combine visits, they are instructed that they will have to perform this visit in the morning after an overnight, 12-hour fast.

Screening Visit (Week 1. Duration: 2 hours): Study participants will be asked to come in during the morning after an overnight, 12-hour fast. During this visit the following will take place:

- **Blood Draw:** A trained phlebotomist (the PI) will draw a fasted blood sample for routine blood work to ensure the participant qualifies for the study. Using a small needle, 15 ml blood will be collected from a vein in the participant's forearm or hand. Blood samples will be sent to LabCorp to be analyzed for HbA1C, Glucose, Basic Metabolic Panel (BMP), and Lipid panel. The blood of women of childbearing potential will be subject to a pregnancy test (hCG) as part of this screening blood draw. This will also occur through LabCorp.
- **Body mass and height.** Height (cm) will be measured without shoes. Body mass (kg) will be measured without shoes, coats, or sweaters. BMI will be calculated as body mass (kg) / height (m)².
- **Blood pressure:** A blood pressure measurement will be taken using an automated upper arm blood pressure monitor (Omron BP5250). A total of three measurements will be taken and the average value of those will be collected for participant characterization.
- **Questionnaires:** Participants will be asked to complete the following questionnaires:
 - *7-day food log:* The seven-day food log will be filled out at home and returned during baseline visit (described below) to provide further insight into the subject's habitual diet.
 - *Food Frequency Questionnaire (FFQ):* The food frequency questionnaires will help identify any dietary restrictions and ensure that the subject's habitual diet meets the inclusion/exclusion criteria.

Baseline Visit 1 (Week 2. Duration: 1 hour): If inclusion/exclusion criteria are met, subjects will be invited for a baseline visit to complete additional measurements. We will ask participants to come in during the morning after an overnight, 12-hour fast. During this visit the following procedures will be performed:

- **Questionnaires:** Participants will be asked to complete the following questionnaires:
 - *Pittsburgh Sleep Quality Index (PSQI):* The Pittsburgh Sleep Quality Index (PSQI) will be used to assess sleep quality and disturbances. This questionnaire will be repeated after each intervention period.
 - *The Perceived Stress Scale (PSS):* PSS evaluates how unpredictable, uncontrollable, and overloaded participants judge their lives. This questionnaire will be repeated after each intervention period.

- *Profile of Mood States (POMS)*: The Profile of Mood States (POMS) 30-item version will determine mood changes using the following domains: Tension-Anxiety, Depression-Dejection, Anger-Hostility, Vigor-Activity, Fatigue-Inertia and Confusion-Bewilderment. This questionnaire will be repeated after each intervention period.
- *Short Form Healthy Survey (SF-36)*: The SF-36 will be used to assess quality of life using physical (functioning, role-physical, pain, general health) and mental domains (vitality, social functioning, role-emotional, and mental health). This questionnaire will be repeated after each intervention period.
- *MacArthur Socio-Economic Status Questionnaire*: This questionnaire determines participants subjective social status questions, as well as educational attainment, occupational status, income, and assets. This information is used for participant characterization and only completed at baseline.
- **Stool and Urine Collection**: Participants will be provided with a urine and stool collection kit to collect first-of-the-day stool and urine samples (see attached). Participants will receive detailed instructions on freezer storage and are provided a cooler with ice packs to bring in the frozen samples during their next visit.
- **Blood Draw**: A trained phlebotomist (the PI) will draw a fasted blood sample for metabolomics and inflammatory biomarker assays. A total of 15 mL of blood (1 TBPS) will be drawn. Our plans for measuring cytokines and metabolites are discussed in the *Analytical Procedures and Statistical Considerations subsection* (see below).

Intervention (44 days x 2 diets; 1 hour per week): After completing all baseline testing, participants will be randomized to one of the two starting diets (agroecological or conventional, for 44 days with a 14 day washout period until they start their second diet (agroecological or conventional depending on the starting diet). In accordance with established protocols, a research dietitian will provide weight-maintenance diets with a macronutrient distribution of 20% protein, 30% fat, and 50% carbohydrate based on each individual's daily energy requirement (Harris-Benedict equation). All foods that participants consume during those 4-weeks will be provided by the Metabolic Kitchen at NDFS, and dietitian-led group classes and handouts with food preparation instructions will be provided to the participants to ensure compliance. The diets will be provided as 4-day rotating menus and participants will be asked to pick-up food twice weekly at the NDFS building. This will allow the research time to interact face-to-face with the participant, address any issues, and further ensure compliance. All subjects assigned to the same diet will receive identical meals and snacks, but portion sizes will be determined based on the previously mentioned daily energy requirement. Food for the agroecological diet will be sourced predominantly from the Greenacres farm (Cincinnati, OH) and food for the conventional diet

will be sourced from local grocery stores (non-organic produce). All foods will be stored in food-grade fridges and freezers in the CHNS Metabolic Kitchen and food boxes will be prepared weekly by staff. Examples of the diets are presented in **Table 2**.

Table 2: Examples of Meals

Breakfast	Whole milk, eggs, oatmeal, and blueberries
Snack	Rice cakes
Lunch	Ground beef, tomato salad and cherries
Snack	Apple with nut butter
Dinner	Grilled chicken with rice and steamed broccoli

Additionally, subjects will complete the following study procedures during each intervention period:

- **Sleep, diet, and activity logs:** We will ask participants to maintain their habitual sleep levels. Participants will be asked to log their wake-up and sleep time as well as the time they spend doing physical activity in RedCap. Participants will be provided a daily link and/or reminded by phone (only if they forgot to fill these out).
- **Stool and urine samples:** Additional stool and urine samples will be collected at the end and beginning of each dietary period, using a similar approach as described in the *baseline visit 1* subsection,
- **Activity:** We will ask participants to maintain their habitual physical activity levels. A commercial Garmin activity monitor will be worn 24 hr/d to record total daily steps as a measure of physical activity. The activity monitor will connect via Bluetooth to the participant's personal smartphone or other internet-connected device loaded with the Garmin Connect app. Data will be stored in individual study accounts on the Garmin website where the study team will be able to access and review activity and monitor device function and provide feedback and encouragement to participants.

Post Diet Visits 1-2 (Weeks 8 & 16; 1 hour): On the last day of each nutrition intervention/diet phase, participants will be asked to come to the CHNS building at Utah State University to undergo a fasted blood draw (30 mL), and to complete questionnaires to determine intervention effects. The blood will be used for cytokines and metabolites and for routine blood samples analysis by LabCorp as described in the *screening visit subsection*. The questionnaires involved include the Perceived Stress Scale (PSS), Short Form Healthy Survey (SF-36), Profile of Mood States (POMS), and the Pittsburgh Sleep Quality Index (PSQI).

Baseline Visit 2 (weeks 8; 1 hour): At the beginning of the second 44-day dietary intervention period, participants will report to the lab facilities within the Center for Human Nutrition at Utah State University after an overnight fast (no eating or drinking except water for 12 h). Participants will be asked to collect fasting urine and first-of-the-day stool samples the morning before coming in, and will undergo a fasted blood draw (30 mL) while in the lab. The blood will be

used for cytokines and metabolites and for routine blood samples analysis by LabCorp as described in the *screening visit subsection*. Participants will also be given detailed instructions on food preparations and provided with their food box for the next 4 days.

